### 5.3 Duration of Therapy

Patients demonstrating clinical benefit, defined as achievement of an objective response (CR, CRi, or PR) or stable disease (SD), may continue therapy for up to 24 cycles (approximately 2 years) of treatment with lenalidomide. Therapy beyond 24 cycles may be considered after discussion with the principal investigator and consultation with the study sponsor.

Investigators are encouraged to keep patients experiencing clinical benefit on study unless significant toxicity puts the subject at risk or routine noncompliance puts the study outcomes at risk. If the subject meets any 1 of the following criteria, withdrawal from treatment is mandatory:

- Disease progression meeting 2008 IWCLL consensus criteria for treatment.
- Intercurrent illness that prevents further lenalidomide administration.
- Any treatment-related Grade 4 non-hematologic toxicity.
- Unacceptable and/or unmanageable Grade  $\geq 3$  toxicity attributable to lenalidomide.
- Any treatment-related hematologic or non-hematologic toxicity delaying treatment more than 14 days.

- Development of autoimmune hemolytic anemia (AIHA) or immune-mediated thrombocytopenia (ITP)
- Subject elects to withdraw from study or becomes pregnant.
- General or specific changes in the patient's condition rendering the patient unacceptable for further treatment in the judgment of the investigator.
- Subject is noncompliant with study procedures and/or scheduled evaluations.
- Investigator considers withdrawal to be in the best interest of the subject.
- Diagnosis of new or secondary malignancies after initiating treatment

Subjects with inadequate study drug compliance (i.e.  $\leq$  80% of planned doses administered) may be replaced.

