#### 5.5 Criteria for Removal from Study

Patients will be removed from treatment when any of the criteria listed in [Section 5.3](#) applies. Irreversible or unacceptable treatment-related toxicities that are Grade  $\geq 3$  as listed in [Section 5.3](#) necessitate discontinuation from study treatment. A patient with a treatment-related Grade  $\geq 3$  adverse event that resolves to Grade  $\leq 1$  within 14 days may continue treatment with appropriate dose reductions as outlined in [Section 6](#). Any Grade 4 toxicity attributable to lenalidomide will require discontinuation from study treatment. The reason for study removal and the date the patient was removed must be documented in the Case Report Form.

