## 6. DOSING DELAYS/DOSE MODIFICATIONS

### 6.1 Dose Modifications due to Toxicity

Because this study assesses the benefits of treating early-stage, asymptomatic CLL/SLL patients who would not otherwise be receiving therapy, the definition of “unacceptable” toxicity will be defined as any treatment-related Grade 4 non-hematologic toxicity or any treatment-related Grade  $\geq 3$  toxicity deemed unmanageable or unacceptable by the patient, his or her treating physician, or the study chair. As described, in [Section 5.3](#) and [Section 5.5](#), unacceptable toxicity will require discontinuation of protocol therapy.

Subjects will be evaluated for adverse events at each visit with the NCI CTEP CTCAE version 5 used as a guide for grading of severity for both hematologic and non-hematologic toxicity.

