### 6.3.10 Infection

It is imperative that accurate reporting of infectious events occur not only as a secondary endpoint of the study, but also so prophylactic therapies (if needed) can be included for future patients enrolled. Infectious toxicity (particularly Grade  $\geq 2$  severity) needs to be recorded and graded in a standard fashion both during treatment and at least every three months following completion of protocol therapy for patients remaining on study. The following information related to all infections must be documented: site of infection (lungs, sinus, skin, blood, urine, fever of unknown origin, etc.), causative agent (type of bacteria, fungus, virus, etc.) if any identified, specific therapeutic interventions. All herpes simplex and varicella zoster cases should be reported and noted as infectious (not skin) toxicities.

- Because infections are an expected complication of CLL, infections occurring in the absence of hematologic toxicity (i.e those not meeting criteria for neutropenic fever) will not require dose reductions.
- For Grade  $\geq 3$  infection, hold lenalidomide and administer medically appropriate therapy. If toxicity resolves to Grade  $\leq 2$  within 2 weeks, then resume lenalidomide at the same dose level.
- Lenalidomide therapy can continue during an episode of Grade  $\leq 2$  infection, so long as infection is adequately controlled.

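### For lenalidomide-related Grade 4 events, the restart rules in 6.3 and the stop rules in 5.3, 5.5 and 6.1 give opposite instructions, and no sentence ranks them

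*Combined protocol and SAP*

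**What the plan says.** **Stop rules.** Section 5.3 introduces its list with "If the subject meets any 1 of the following criteria, withdrawal from treatment is mandatory". The list includes "Any treatment-related Grade 4 non-hematologic toxicity" and "Any treatment-related hematologic or non-hematologic toxicity delaying treatment more than 14 days". Section 6.1 repeats the first of these: unacceptable "toxicity will be defined as any treatment-related Grade 4 non-hematologic toxicity", among other events, and "unacceptable toxicity will require discontinuation of protocol therapy". Section 5.5 lets a related event of Grade 3 or higher that resolves to Grade 1 or lower "within 14 days may continue treatment with appropriate dose reductions" under Section 6. Its next sentence reads "Any Grade 4 toxicity attributable to lenalidomide will require discontinuation from study treatment", with no limit to non-hematologic events.

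**Restart rules.**
- 6.3.10 (infection, Grade 3 or higher, no attribution test): hold, and on recovery to Grade 2 or lower "within 2 weeks, then resume lenalidomide at the same dose level".
- 6.3.9 (tumor lysis above Grade 2): hold, then restart at the current dose after a first episode and at the next lower level after a repeat at the same dose.
- 6.3.4 (other rash, Grade 3 or higher) and 6.3.12 (other related non-hematologic toxicity, Grade 2 or higher): resume at the next lower level if resolved to Grade 1 or lower within two weeks.
- 6.3.1 (related hematologic toxicity, Grade 3 or higher): the same. The current amendment adds that White Blood Cell Decreased and Lymphocyte Count Decreased need no modification.

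The opening of 6.3 presents these as the specific criteria for holding and modifying dose. It does not make them subject to 5.3, 5.5 or 6.1.

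**The concern.** A range written as Grade 3 or higher, or above Grade 2, includes Grade 4. None of 6.3.4, 6.3.9, 6.3.10 and 6.3.12 excludes Grade 4 or refers back to the stop rules, and none of 5.3, 5.5 and 6.1 makes an exception for infection, lysis or rash. A related Grade 4 event in these categories therefore meets a restart rule and a stop rule at once. A site that goes straight to the event-specific subsection and follows it literally would re-dose a patient whose treatment three other sections end.

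Section 6.1 justifies its strict limit by the population: early-stage, asymptomatic patients who would otherwise be untreated. Related cases are foreseeable, because the lenalidomide adverse event list in 7.1 names both infection and tumor lysis as possibly related.

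The hematologic side has the opposite problem. Taken literally, 5.5 ends treatment for a related Grade 4 fall in lymphocytes, which 6.3.1 describes as an expected therapeutic outcome.

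**Working it through.** No calculated figure is involved; the check is to apply each rule to the same case. All cases are lenalidomide-related unless stated. The days are illustrative, counted from the hold. Dose levels are from Table 4 (5 mg daily, then 2.5 mg daily).

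| Case | 6.3 instruction | Stop rules | Can both be obeyed? |
|---|---|---|---|
| Grade 4 infection, Grade 2 on day 10 | 6.3.10: resume, same dose | 5.3, 5.5, 6.1: discontinue | No |
| Grade 4 lysis on 5 mg, first episode, electrolytes Grade 1 on day 10 | 6.3.9: restart at 5 mg | 5.3, 5.5, 6.1: discontinue | No |
| Same, repeat episode at 5 mg | 6.3.9: restart at 2.5 mg daily | 5.3, 5.5, 6.1: discontinue | No |
| Grade 4 event under 6.3.4 or 6.3.12, Grade 1 on day 10 | Resume at next lower level | 5.3, 5.5, 6.1: discontinue | No |
| Grade 4 platelet decrease on 5 mg, Grade 1 on day 10 | 6.3.1: resume at 2.5 mg daily | 5.5 discontinues; 5.3 and 6.1 have no automatic stop | No |
| Grade 4 lymphocyte decrease | 6.3.1: no modification | 5.5 discontinues; 5.3 and 6.1 have no automatic stop | No |
| Grade 3 lysis, electrolytes Grade 1 on day 20 | 6.3.9: restart, no time limit given | 5.3 withdraws, since 20 > 14 days | Yes: 6.3.9 is silent on duration and 5.3 supplies the limit |
| Grade 3 infection, Grade 2 on day 12 | 6.3.10: resume, same dose | None triggered: not Grade 4, and 12 ≤ 14 days | Yes, if not judged unacceptable or unmanageable |
| Unrelated Grade 4 infection, Grade 2 on day 10 | 6.3.10: resume, same dose | None triggered | Yes |

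Two separate faults follow.

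1. For non-hematologic events the conflict lies only at related Grade 4, where three stop rules oppose each restart rule.
2. For hematologic events 5.5 stands alone against 6.3.1, because 5.3 and 6.1 confine their automatic Grade 4 stop to non-hematologic toxicity.

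There is also a smaller mismatch. Section 6.3.10 allows dosing through a controlled infection of Grade 2 or lower, while 6.2 requires any drug-related event to be Grade 1 or lower on day 1 of a cycle. A related, controlled Grade 2 infection that is present on day 1 passes one rule and fails the other.

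**The case against.** The strongest reply is that precedence is already clear. Section 5.3 uses mandatory language. Section 6.1 opens Section 6 and cites 5.3 and 5.5. Section 5.5 points to Section 6 for dose reductions and then immediately limits it with the Grade 4 sentence. For non-hematologic events this is the natural reading, and it stands as such. It remains an inference, however, since nothing says the 6.3 rules are subject to the others. Nor can it be applied to 5.5 as written, because letting 5.5 prevail over all of Section 6 would override 6.3.1, including the exemption just added. Precedence has to be written down.

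The reply also limits the practical impact, with reason. Under 7.5.2.1, events of Grade 2 or higher go to the principal investigator immediately, and 7.3 requires expedited reports for Grade 4 events. A re-dosing decision is unlikely to pass unseen.

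Several stronger readings are tempting but not supported:
- *That the protocol intends re-dosing after related Grade 4 events, because 6.3.3 and 6.3.6 write their own stop rules and 6.3.9 and 6.3.10 do not.* Those two sections stop at Grade 3, which is stricter than the general rule, so they had to be spelled out. Silence elsewhere fits reliance on 6.1.
- *That the missing time limits in 6.3.8 (tumor flare) and 6.3.9 contradict 5.3.* Neither section permits an indefinite delay, and the 14-day rule in 5.3 applies to any related toxicity.
- *That 5.5 forbids resuming after a Grade 3 infection that has fallen only to Grade 2.* The 5.5 sentence is permissive. It says which patients may continue, not that all others must stop.

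**Conclusion.** The text is wrong as written on two counts, and a wording correction should be made. First, a related Grade 4 infection, tumor lysis, or event under 6.3.4 or 6.3.12 receives both a restart and a discontinue instruction, with no stated precedence. Second, the Grade 4 sentence of 5.5 is wider than 5.3 and 6.1 and contradicts 6.3.1. The 6.2 mismatch for controlled infection is a lesser clarification.

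The scope is narrow. Unrelated events raise no conflict, and related Grade 3 events raise none over the Grade 4 stop. The number of patients affected cannot be derived: 7.1 gives no frequency by grade, and Section 9 says only that few patients remain on treatment. Since the Schema ties lysis precautions to the first lenalidomide cycle, infection is the more likely trigger in continuing patients. The conclusion assumes that a lenalidomide-attributed event counts as treatment-related under 5.3 and 6.1. It does not claim that any patient has been re-dosed wrongly.

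**What to change.** 1. At the head of 6.3, state that the mandatory discontinuation rules in 5.3 and 6.1 (related Grade 4 non-hematologic toxicity; related treatment delay over 14 days) prevail over every restart instruction in 6.3. This also settles 6.3.4 and 6.3.12.
2. In 6.3.9 and 6.3.10, limit the restart rules to Grade 3 events or events not attributed to lenalidomide.
3. Insert the word non-hematologic in the Grade 4 sentence of 5.5, so that it matches 5.3, 6.1 and 6.3.1. Do not instead cap 6.3.1 at Grade 3. Neutrophil and platelet decreases are in the above-20% column of 7.1, and a cap would withdraw patients whom 6.3.1 now allows to resume at a lower dose. That would be a substantive change which 5.3 does not require.
4. As a lesser item, write the exception for controlled infection of Grade 2 or lower into 6.2.

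The cost is a wording amendment, with no new data, visits or patients. The rare patient with a related Grade 4 infection or lysis is withdrawn, as 5.3 already requires. Under item 3, related Grade 4 hematologic events are governed by 6.3.1, with its hold, dose reduction and two-week limit, and by the judgement-based Grade 3 or higher criterion in 5.3 and 6.1.

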#### 6.3.11 Abnormal Menstruation or Pregnancy Test

If a female study patient misses a period, or for abnormal menstrual bleeding or abnormal pregnancy test, obtain a serum pregnancy test. Hold lenalidomide therapy until pregnancy is excluded. Discontinue protocol therapy if pregnancy test is positive. See [Section 7.7](#) for further information regarding management and reporting requirements pertaining to pregnancy occurring during lenalidomide treatment.

#### 6.3.12 Other Non-Hematologic Toxicity

- In the instance of Grade  $\geq 2$  lenalidomide-related non-hematologic toxicity on day 1 of a cycle, delay lenalidomide therapy and monitor at least weekly. If toxicity resolves to Grade  $\leq 1$  within 2 weeks, then resume lenalidomide at the next lower dose level.
- If Grade  $\geq 2$  lenalidomide-related non-hematologic toxicity occurs during a cycle, delay lenalidomide therapy and monitor at least weekly. If toxicity resolves to Grade  $\leq 1$  within 2 weeks, then resume lenalidomide at the next lower dose level.
- If treatment is delayed for more than 2 weeks, discontinue protocol therapy

### 6.4 Intrasubject Escalation

As described previously in **5.1.1**, the dose of lenalidomide may be increased to 5 mg/day beginning as early as the second treatment cycle if all of the following criteria are met:

- No clinically significant Grade 3 or greater non-hematologic toxicities attributable to lenalidomide during the preceding cycle.
- Any lenalidomide-associated hematologic toxicity has resolved to Grade  $\leq 1$  severity.
- Maintained platelet count  $>50K$  at all times during the previous cycle.
- Maintained ANC  $>1K$  at all times during the preceding cycle.
- Any other drug-related adverse events have resolved to Grade  $\leq 1$  severity.

Patients not meeting criteria for dose escalation upon beginning the second cycle of

lenalidomide can be re-evaluated for dose escalation at the start of subsequent cycles, at which time the same criteria will apply. Dose escalation beyond 5 mg/day will not be permitted so as to limit the risk in this patient population who would not otherwise be receiving therapy.

If the lenalidomide dose has been reduced for toxicity, dose re-escalation is permitted if the patient has tolerated the reduced dose for greater than one cycle. The patient will then be re-evaluated for dose escalation at the beginning of each subsequent cycle of therapy according to the parameters detailed above. If the patient subsequently develops toxicity requiring dose reduction, no further attempts at dose escalation will be permitted.

## 7. ADVERSE EVENTS: LIST AND REPORTING REQUIREMENTS

Adverse event (AE) monitoring and reporting is a routine part of every clinical trial. The following list of AEs (07.1.1) and the characteristics of an observed AE (Section 7.2) will determine whether the event requires expedited (via CTEP-AERS) reporting **in addition** to routine reporting.

### 7.1 CAEPR for Lenalidomide

#### Comprehensive Adverse Events and Potential Risks list (CAEPR) for Lenalidomide (CC-5013, NSC 703813)

The Comprehensive Adverse Events and Potential Risks list (CAEPR) provides a single list of reported and/or potential adverse events (AE) associated with an agent using a uniform presentation of events by body system. In addition to the comprehensive list, a subset, the Specific Protocol Exceptions to Expedited Reporting (SPEER), appears in a separate column and is identified with bold and italicized text. This subset of AEs (SPEER) is a list of events that are protocol specific exceptions to expedited reporting to NCI (except as noted below). Refer to the 'CTEP, NCI Guidelines: Adverse Event Reporting Requirements' [http://ctep.cancer.gov/protocolDevelopment/electronic\\_applications/docs/aeguidelines.pdf](http://ctep.cancer.gov/protocolDevelopment/electronic_applications/docs/aeguidelines.pdf) for further clarification. *Frequency is provided based on 4081 patients.* Below is the CAEPR for Lenalidomide (CC-5013).

**NOTE:** Report AEs on the SPEER **ONLY IF** they exceed the grade noted in parentheses next to the AE in the SPEER. If this CAEPR is part of a combination protocol using multiple investigational agents and has an AE listed on different SPEERs, use the lower of the grades to determine if expedited reporting is required.

Version 2.8, June 27, 2019

Adverse Events with Possible Relationship to Lenalidomide (CC-5013) (CTCAE 5.0 Term) [n= 4081]			Specific Protocol Exceptions to Expedited Reporting (SPEER)
Likely (>20%)	Less Likely (<=20%)	Rare but Serious (<3%)	
BLOOD AND LYMPHATIC SYSTEM DISORDERS			
Anemia			Anemia (Gr 3)

Adverse Events with Possible Relationship to Lenalidomide (CC-5013) (CTCAE 5.0 Term) [n= 4081]			Specific Protocol Exceptions to Expedited Reporting (SPEER)
Likely (>20%)	Less Likely (<=20%)	Rare but Serious (<3%)	
	Blood and lymphatic system disorders - Other (pancytopenia)		
	Febrile neutropenia		
	Hemolysis		
CARDIAC DISORDERS			
		Atrial fibrillation	
		Heart failure	
		Myocardial infarction 	
EAR AND LABYRINTH DISORDERS			
	Vertigo		
ENDOCRINE DISORDERS			
		Hyperthyroidism	
	Hypothyroidism		Hypothyroidism (Gr 3)
EYE DISORDERS			
	Blurred vision		
	Cataract		
GASTROINTESTINAL DISORDERS			
	Abdominal pain		
Constipation			Constipation (Gr 3)
Diarrhea			Diarrhea (Gr 3)
	Dry mouth		
	Dyspepsia		
	Nausea		Nausea (Gr 3)
	Vomiting		Vomiting (Gr 3)
GENERAL DISORDERS AND ADMINISTRATION SITE CONDITIONS			
	Chills		Chills (Gr 2)
	Edema limbs		Edema limbs (Gr 3)
Fatigue			Fatigue (Gr 3)
	Fever		Fever (Gr 3)
	Generalized edema		
	Non-cardiac chest pain		
	Pain		
HEPATOBILIARY DISORDERS			
		Hepatic failure	
		Hepatobiliary disorders - Other (cholestasis)	
IMMUNE SYSTEM DISORDERS			
		Allergic reaction	
		Anaphylaxis	
		Immune system disorders - Other (angioedema)	
		Immune system disorders - Other (graft vs. host disease) 	
INFECTIONS AND INFESTATIONS			
	Infection 		Infection (Gr 3)
INJURY, POISONING AND PROCEDURAL COMPLICATIONS			

Adverse Events with Possible Relationship to Lenalidomide (CC-5013) (CTCAE 5.0 Term) [n= 4081]			Specific Protocol Exceptions to Expedited Reporting (SPEER)
Likely (>20%)	Less Likely (<=20%)	Rare but Serious (<3%)	
	Bruising		
	Fall		
INVESTIGATIONS			
	Alanine aminotransferase increased		
	Alkaline phosphatase increased		
	Aspartate aminotransferase increased		
	Blood bilirubin increased		
	GGT increased		
	Investigations - Other (C-Reactive protein increased)		
		Lipase increased	
	Lymphocyte count decreased		Lymphocyte count decreased (Gr 4)
Neutrophil count decreased			Neutrophil count decreased (Gr 4)
Platelet count decreased			Platelet count decreased (Gr 4)
	Weight loss		Weight loss (Gr 2)
	White blood cell decreased		White blood cell decreased (Gr 4)
METABOLISM AND NUTRITION DISORDERS			
	Anorexia		Anorexia (Gr 3)
	Dehydration		
	Hyperglycemia		
	Hyperuricemia		
	Hypocalcemia		
	Hypokalemia		
	Hypomagnesemia		
	Hyponatremia		
	Hypophosphatemia		
	Iron overload		
		Tumor lysis syndrome	
MUSCULOSKELETAL AND CONNECTIVE TISSUE DISORDERS			
	Arthralgia		
	Back pain		
	Bone pain		
	Generalized muscle weakness		
	Muscle cramp		Muscle cramp (Gr 2)
	Myalgia		Myalgia (Gr 2)
	Pain in extremity		
		Rhabdomyolysis 	
NEOPLASMS BENIGN, MALIGNANT AND UNSPECIFIED (INCL CYSTS AND POLYPS)			
		Leukemia secondary to oncology chemotherapy 	
		Myelodysplastic syndrome 	

Adverse Events with Possible Relationship to Lenalidomide (CC-5013) (CTCAE 5.0 Term) [n= 4081]			Specific Protocol Exceptions to Expedited Reporting (SPEER)
Likely (>20%)	Less Likely (<=20%)	Rare but Serious (<3%)	
		Neoplasms benign, malignant and unspecified (incl cysts and polyps) - Other (tumor flare) 	
		Neoplasms benign, malignant and unspecified (incl cysts and polyps) - Other (second primary malignancies)	
		Treatment related secondary malignancy 	
NERVOUS SYSTEM DISORDERS			
	Dizziness		
	Depressed level of consciousness		
	Dysesthesia		
	Dysgeusia		
	Headache		
	Paresthesia		
	Peripheral motor neuropathy		
	Peripheral sensory neuropathy		
		Stroke 	
	Syncope		
	Tremor		
PSYCHIATRIC DISORDERS			
	Depression		
	Insomnia		Insomnia (Gr 2)
	Psychiatric disorders - Other (mood altered)		
RENAL AND URINARY DISORDERS			
		Acute kidney injury	
RESPIRATORY, THORACIC AND MEDIASTINAL DISORDERS			
	Cough		Cough (Gr 2)
	Dyspnea		Dyspnea (Gr 3)
	Epistaxis		
		Pneumonitis	
SKIN AND SUBCUTANEOUS TISSUE DISORDERS			
	Dry skin		
		Erythema multiforme	
	Hyperhidrosis		Hyperhidrosis (Gr 2)
	Pruritus		Pruritus (Gr 2)
	Rash maculo-papular		Rash maculo-papular (Gr 3)
		Skin and subcutaneous tissue disorders - Other (drug reaction with eosinophilia and systemic symptoms [DRESS])	
	Skin and subcutaneous tissue disorders - Other (pyoderma gangrenosum)		
		Stevens-Johnson syndrome	

Adverse Events with Possible Relationship to Lenalidomide (CC-5013) (CTCAE 5.0 Term) [n= 4081]			Specific Protocol Exceptions to Expedited Reporting (SPEER)
Likely (>20%)	Less Likely (<=20%)	Rare but Serious (<3%)	
SURGICAL AND MEDICAL PROCEDURES			Toxic epidermal necrolysis
		Surgical and medical procedures - Other (impaired stem cell mobilization) 	
VASCULAR DISORDERS			
	Hematoma		
	Hypertension		
	Hypotension		
	Peripheral ischemia		
	Thromboembolic event 		Thromboembolic event (Gr 3)
	Vasculitis		

This table will be updated as the toxicity profile of the agent is revised. Updates will be distributed to all Principal Investigators at the time of revision. The current version can be obtained by contacting [[contact]](mailto:[contact]). Your name, the name of the investigator, the protocol and the agent should be included in the e-mail.

Myocardial infarction and cerebrovascular accident (stroke) have been observed in multiple myeloma patients treated with lenalidomide and dexamethasone.

Graft vs. host disease has been observed in subjects who have received lenalidomide in the setting of allo-transplantation.

Infection includes all 75 sites of infection under the INFECTIONS AND INFESTATIONS SOC.

The rare adverse event of rhabdomyolysis has been observed with lenalidomide. The reports of rhabdomyolysis were confounded by concurrent use of statins and dexamethasone, concurrent viral and bacterial infections, trauma, and serotonin syndrome. Statins, infections, trauma, and serotonin syndrome are known risk factors for rhabdomyolysis.

There has been an increased frequency of secondary malignancies (SPM) including ALL, AML, and MDS, and certain other types of cancers of the skin and other organs in multiple myeloma (MM) patients being treated with melphalan, prednisone, and lenalidomide post bone marrow transplant. The use of lenalidomide in cancers other than MM, shows that invasive SPMs occurred in a small number of patients. Patients treated with lenalidomide should be closely followed for the occurrence of SPMs.

Serious tumor flare reactions have been observed in patients with chronic lymphocytic leukemia (CLL) and lymphoma.

A decrease in the number of stem cells (CD34+ cells) collected from patients treated with >4 cycles of lenalidomide has been reported.

Significantly increased risk of deep vein thrombosis (DVT), pulmonary embolism (PE), and arterial thrombosis has been observed in patients with multiple myeloma receiving lenalidomide with dexamethasone.

Gastrointestinal hemorrhage includes: Anal hemorrhage, Cecal hemorrhage, Colonic hemorrhage, Duodenal hemorrhage, Esophageal hemorrhage, Esophageal varices hemorrhage, Gastric hemorrhage,

Hemorrhoidal hemorrhage, Ileal hemorrhage, Intra-abdominal hemorrhage, Jejunal hemorrhage, Lower gastrointestinal hemorrhage, Oral hemorrhage, Pancreatic hemorrhage, Rectal hemorrhage, Retroperitoneal hemorrhage, and Upper gastrointestinal hemorrhage under the GASTROINTESTINAL DISORDERS SOC.

Gastrointestinal obstruction includes: Colonic obstruction, Duodenal obstruction, Esophageal obstruction, Ileal obstruction, Jejunal obstruction, Obstruction gastric, Rectal obstruction, and Small intestinal obstruction under the GASTROINTESTINAL DISORDERS SOC.

Osteonecrosis of the jaw has been seen with increased frequency when lenalidomide is used in combination with bevacizumab, docetaxel (Taxotere®), prednisone, and zolendronic acid (Zometa®).

**NOTE:** While not observed in human subjects, lenalidomide, a thalidomide analogue, caused limb abnormalities in a developmental monkey study similar to birth defects caused by thalidomide in humans. If lenalidomide is used during pregnancy, it may cause birth defects or embryo-fetal death. Pregnancy must be excluded before start of treatment. Prevent pregnancy during treatment by the use of two reliable methods of contraception.

**NOTE:** In a trial of first line treatment of patients with chronic lymphocytic leukemia (CLL), single agent lenalidomide (CC-5013) increased the risk of death as compared to control arm (chlorambucil).

**NOTE:** In two randomized trials of patients with multiple myeloma (MM), the addition of MK-3475 (pembrolizumab) to a thalidomide analog plus dexamethasone, resulted in increased mortality. Treatment of patients with MM with a PD-1 or PD-L1 blocking antibody, such as MK-3475 (pembrolizumab), in combination with a thalidomide analog, such as lenalidomide, is not recommended outside of controlled clinical trials.

**NOTE:** In a clinical trial in patients with Mantle cell lymphoma (MCL), there was an increase in early deaths (within 20 weeks); 12.9% in the lenalidomide (CC-5013) arm vs. 7.1% in the control arm.

**Adverse events reported on lenalidomide (CC-5013) trials, but for which there is insufficient evidence to suggest that there was a reasonable possibility that lenalidomide (CC-5013) caused the adverse event:**

**BLOOD AND LYMPHATIC SYSTEM DISORDERS** - Blood and lymphatic system disorders - Other (monocytosis); Disseminated intravascular coagulation; Eosinophilia

**CARDIAC DISORDERS** - Atrial flutter; Atrioventricular block first degree; Cardiac arrest; Cardiac disorders - Other (cardiovascular edema); Cardiac disorders - Other (ECG abnormalities); Chest pain - cardiac; Left ventricular systolic dysfunction; Palpitations; Pericarditis; Sinus bradycardia; Sinus tachycardia; Supraventricular tachycardia; Ventricular tachycardia

**EAR AND LABYRINTH DISORDERS** - Tinnitus

**ENDOCRINE DISORDERS** - Cushingoid

**EYE DISORDERS** - Dry eye; Flashing lights; Retinopathy

**GASTROINTESTINAL DISORDERS** - Abdominal distension; Anal mucositis; Ascites; Colonic perforation; Dysphagia; Flatulence; Gastroesophageal reflux disease; Gastrointestinal disorders - Other (Crohn's disease aggravated); Gastrointestinal disorders - Other (diverticulitis); Gastrointestinal disorders - Other (pale feces); Gastrointestinal hemorrhage; Gastrointestinal obstruction; Ileus; Mucositis oral; Pancreatitis; Rectal mucositis; Small intestinal mucositis

**GENERAL DISORDERS AND ADMINISTRATION SITE CONDITIONS** - Malaise; Multi-organ failure

**HEPATOBILIARY DISORDERS** - Cholecystitis

**INFECTIONS AND INFESTATIONS** - Conjunctivitis; Infections and infestations - Other (opportunistic infection associated with >=Grade 2 Lymphopenia); Myelitis

**INJURY, POISONING AND PROCEDURAL COMPLICATIONS** - Fracture; Hip fracture; Vascular access complication

**INVESTIGATIONS** - Activated partial thromboplastin time prolonged; Cholesterol high; Creatinine increased; Electrocardiogram QT corrected interval prolonged; INR increased; Investigations - Other (hemochromatosis)

**METABOLISM AND NUTRITION DISORDERS** - Acidosis; Hypercalcemia; Hyperkalemia; Hypoglycemia

**MUSCULOSKELETAL AND CONNECTIVE TISSUE DISORDERS** - Arthritis; Chest wall pain; Joint effusion; Muscle weakness lower limb; Neck pain; Osteonecrosis of jaw

**NEOPLASMS BENIGN, MALIGNANT AND UNSPECIFIED (INCL CYSTS AND POLYPS)** - Tumor pain

**NERVOUS SYSTEM DISORDERS** - Ataxia; Cognitive disturbance; Dysphasia; Edema cerebral; Encephalopathy; Intracranial hemorrhage; Ischemia cerebrovascular; Leukoencephalopathy; Memory impairment; Nervous system disorders - Other (hyporeflexia); Spinal cord compression; Seizure; Somnolence; Transient ischemic attacks

**PSYCHIATRIC DISORDERS** - Agitation; Anxiety; Confusion; Psychosis

**RENAL AND URINARY DISORDERS** - Urinary frequency; Urinary incontinence; Urinary tract pain

**REPRODUCTIVE SYSTEM AND BREAST DISORDERS** - Reproductive system and breast disorders - Other (hypogonadism); Vaginal hemorrhage

**RESPIRATORY, THORACIC AND MEDIASTINAL DISORDERS** - Adult respiratory distress syndrome; Allergic rhinitis; Atelectasis; Bronchopulmonary hemorrhage; Hypoxia; Laryngeal mucositis; Pharyngeal mucositis; Pleural effusion; Pulmonary hypertension; Respiratory failure; Tracheal mucositis; Voice alteration

**SKIN AND SUBCUTANEOUS TISSUE DISORDERS** - Alopecia; Nail loss; Photosensitivity; Rash

acneiform; Skin and subcutaneous tissue disorders - Other (Sweet's Syndrome); Urticaria

**VASCULAR DISORDERS** - Hot flashes; Phlebitis; Vascular disorders - Other (hemorrhage NOS)

**Note:** Lenalidomide (CC-5013) in combination with other agents could cause an exacerbation of any adverse event currently known to be caused by the other agent, or the combination may result in events never previously associated with either agent.

